JUVÉDERM VOLITE XC injectable gel will be administered using a 32 G 1/2" or a 32 G 3/16" needle in multiple microdepot injections across both cheeks. At initial and repeat (if performed) treatments, volume is not to exceed a total of 4 mL for both cheeks. At optional touch-up procedure, volume is not to exceed 2 mL for both cheeks. Needle length selection, total injection volume, and injection spacing will be determined by the TI.
DURATION OF STUDY: Treatment group: up to 1 month for screening, up to 1 month for treatment, 6 months of follow-up, and 4 months of follow-up after optional repeat treatment. Control group: up to 1 month for screening and 1 month of follow-up; up to 1 month for treatment and 6 months of follow-up after optional treatment.
OBJECTIVES: The objective of this study is to evaluate the safety and effectiveness of JUVÉDERM VOLITE XC injectable gel for the improvement in cheek skin smoothness.
KEY ENDPOINTS: 
 Primary: ACSS responder status at Month 1 Secondary: Change from baseline to Month 1 on FACE-Q Satisfaction with Skin questionnaire Secondary: AFLS responder status at Month 1 Safety: FACE- Recovery Early Life Impact questionnaire, procedural pain, ISRs from 30-day e-diaries, AIs, Snellen visual acuity, confrontation visual fields, and ocular motility
OVERALL STUDY DESIGN: 
 Randomized, controlled, parallel-design Single-blind: EI s are blinded; TIs and subjects are not blinded Treatment group subjects receive initial treatment and optional touch-up treatment at 30 days if needed to achieve optimal correction. Follow-up visits are 3 days after each treatment (safety only) and at Months 1, 2, 4, and 6 after last treatment. Subjects exit the study at Month 6 or receive repeat treatment and are followed at Day 3 and Months 1 and 4 after repeat treatment. Control group subjects are followed for 1 month after randomization (no-treatment control period) and then either exit the study or receive optional treatment (initial and touch-up, if needed) in the delayed treatment period. Follow-up visits are 3 days after each treatment (safety only) and at Months 1, 2, 4, and 6 after last treatment. Subjects exit the study at Month 6.

DIAGNOSIS AND CRITERIA FOR INCLUSION/EXCLUSION:

Adults seeking improvement in cheek skin smoothness

INCLUSION:

1. Age 22 or over and in good general health

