5.1 Overall Design

[figure not shown]
This is a multicenter, evaluator-blind, controlled, parallel-design, prospective study of adults seeking improvement in cheek skin smoothness. Up to 20 investigational sites will enroll and follow subjects who meet the study criteria according to the study design in [Figure 5-1](#). Each site will have a PI who is responsible for the overall conduct of the study at that site and may also be the TI. The TI performs all study treatments, and the blinded EI evaluates ACSS, AFLS, and skin hydration measurements.

The study will span a total of approximately 20 months: an estimated 9 months for recruitment and 11 months for follow-up. For the treatment group, each subject's participation will encompass up to 30 days of treatment and up to 10 months of follow-up (6 months for those choosing not to receive repeat treatment at Month 6). For the control group, each subject's participation will encompass 1 month; for control subjects who opt to receive treatment, the treatment period will be up to 30 days, and the follow-up period will be up to 6 months.

Treatment group subjects receive initial treatment and optional touch-up treatment at 30 days if needed to achieve optimal correction. Follow-up visits are 3 days after each treatment (safety only) and at Months 1, 2, 4, and 6 after last treatment. Subjects exit the study at Month 6 or receive repeat treatment and are followed at Day 3 and Months 1 and 4 after repeat treatment. Control group subjects are followed for 1 month after randomization (no-treatment control period) and then either exit the study or receive optional treatment (initial and touch-up, if needed) in the delayed treatment period. Post-treatment follow-up visits are 3 days after each treatment and at Months 1, 2, 4, and 6 after last treatment.

To ensure adequate enrollment of subjects with Fitzpatrick skin phototype V and VI, up to 10 subjects may be enrolled in the Fitzpatrick V/VI safety cohort with less stringent inclusion criteria (see [Section 6.1](#)) and followed for safety only.

Figure 5-1 Study Design

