1.2. Study Design

[figure not shown]
Study 1867-701-008 is a multicenter, evaluator-blind, controlled, parallel-design, prospective study of adults seeking improvement in cheek skin smoothness. The cheek skin smoothness will be assessed based on ACSS scores, ranging from 0 to 4 (none to extreme). Participants randomized to JUVÉDERM VOLITE XC will receive injectable gel in multiple microdepot injections across both cheeks. The following treatment groups are defined for this study:

- VOLITE: JUVÉDERM VOLITE™ XC injectable gel
- Control: No-treatment

Up to 263 participants will be enrolled, and approximately 210 participants from maximum 20 investigational sites will be randomized at a 2:1 ratio to treatment group and control group. Each site will have a blinded evaluating investigator (EI) and a principal investigator (PI) who is responsible for the overall conduct of the study at that site and may also be the treating investigator (TI). The TI performs all study treatments, and the blinded EI evaluates ACSS, AFLS, and skin hydration measurements.

The study design is presented in [Figure 1-1](#). Treatment group participants receive initial treatment and optional touch-up treatment at 30 days if needed to achieve optimal correction. Follow-up visits are 3 days after each treatment (collection of only safety data) and at Months 1, 2, 4, and 6 after the preceding treatment. Participants exit the study at Month 6 or receive repeat treatment and are followed at Day 3 and Months 1 and 4 after repeat treatment. Control group participants are followed for 1 month after randomization (the ‘no-treatment control’ period) and then either exit the study or receive optional treatment (initial and touch-up, if needed) in the delayed treatment period. Post-treatment follow-up visits are 3 days after each treatment and at Months 1, 2, 4, and 6 after the preceding treatment.

To ensure adequate enrollment of participants with Fitzpatrick skin phototype V and VI, up to 10 participants may be enrolled in the Fitzpatrick V/VI safety cohort with less stringent inclusion criteria (see protocol [Section 6.1](#)) and followed for safety only.

Figure 1-1 Study Design

2. Statistical Hypotheses

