5.1. General Considerations

- The primary analysis will be performed after the database is locked and randomization schedule is released.
- To account for different timing of VOLITE treatment and comparable time frame of data collection to enhance interpretability of effectiveness and safety analyses, the statistical analyses will be performed by the study periods defined below in [Table 5-1](#). For participants randomized to the treatment group, the Treated Period (TP) is the Control Period (CP) plus the Follow-up Period; for participants randomized to the control group, the TP is the Follow-up Period composed of the delayed treatment period plus the delayed treatment follow-up period ([Figure 1-1](#)). Follow-up Period starts on the end date of CP + 1 and ends on the same day as TP.

Table 5-1 Definition of the Control, Treatment, and Repeat Treatment Periods by Randomization Group

Randomization Group	Period	Treatment Group Label	Start Date	End Date
Treatment	Control Period (CP)	VOLITE	Initial treatment date	
The end date is the date of the Month 1 assessment:
 
 • If multiple assessments fall into Month 1 window, the date of the assessment included in the Month 1 analysis will be used as end date. • For participants who exit before Month 1, the end date is study exit date. • For participants with a missing assessment at Month 1, the end date is the target day for Month 1.
	Treated Period (TP)	VOLITE	Initial treatment date	Date of repeat treatment or the study exit date, whichever is earlier
	Repeat Treatment Period (RP)	VOLITE	Repeat treatment date	Study exit date
Control	CP	Control	Randomization date	
For participants who do not receive optional treatment:
 
 • If multiple assessments fall into Month 1 window, the date of the assessment included in the Month 1 analysis will be used as end date. • For participants who exit before Month 1, the end date is study exit date. • For participants with missing assessment at Month 1, the target day for Month 1 (Day 31) will be the end date. 
For participants who receive optional treatment: the end date is the date of optional treatment.

	TP	VOLITE Post-Control	Optional treatment date	Study exit date

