5.6.3. Adverse Events

An AE will be considered a treatment emergent adverse event (TEAE) if the AE began or worsened (increased in severity or became serious) after first administration of VOLITE for the treatment group and after the date of randomization for the control group. A TESAE is defined as an SAE that is also a TEAE. Overall summary will be provided on a per-participant level for TEAEs, treatment-related TEAEs, TESAEs, deaths, and TEAEs leading to study intervention discontinuation.

If more than one event is coded to the same PT for the same participant, the participant will be counted only once for that PT using the greatest severity for the summarizations by severity and most related occurrence for the summarizations by relationship to study intervention. If the severity of a TEAE is missing, the maximum severity will be assigned to the event for the summarization by severity. The value will be displayed as missing in the data listing. If the relationship to the study intervention is missing for a TEAE, the event will be considered related to the study intervention for the summarization. The value will be displayed as missing in the data listing.

TEAEs will be summarized by treatment group for CP using the Safety population. TEAEs will also be summarized for TP and RP using the VT and VRT populations, respectively.

The number and percentage of participants with TEAEs and the events in the following AE categories will be summarized for the above populations as described in [Table 5-8](#). For participants who received repeat treatment, their AEs reported during the first month in the initial treatment period will be summarized and presented in parallel with AEs reported during the repeat treatment period.

JUVÉDERM VOLITE™ XC

Summary tables will be provided for participants with TESAEs and participants with TEAEs leading to discontinuation if these occurred in 5 or more participants. Listings of all TEAEs, AESIs, TESAEs, TEAEs leading to discontinuation, and death will be presented.

Table 5-8 **TEAE Summaries**

Endpoint	Description	Timing	Methodology

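### The one AE summary that sets repeat against initial treatment in the same participants compares about 1 month with about 4 months, which tilts it against repeat treatment

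*SAP*

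**What the plan says.** SAP 5.6.3 (Adverse Events) states that, for participants given repeat treatment, adverse events "reported during the first month in the initial treatment period will be summarized and presented in parallel with AEs reported during the repeat treatment period". The first column is cut at one month. The second carries no such limit.

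SAP Table 5-1 (section 5.1) gives the start and end of the repeat treatment period (RP) as "Repeat treatment date Study exit date". The protocol synopsis allows "4 months of follow-up after optional repeat treatment", and SAP 1.2 says that these participants "are followed at Day 3 and Months 1 and 4 after repeat treatment". Table 5-1 defines no period called the initial treatment period. The plain reading of its first month is the month that follows the initial injection.

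SAP Table 5-8 reports TEAEs by counts and percentages for the control, treated and repeat periods (CP, TP and RP). It gives no person-time rate and no first-month cut of the RP.

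**The concern.** A reader will use this display to ask whether a second course is as well tolerated as the first. It is the only AE summary that the SAP explicitly presents in parallel in the same repeat-treated participants, so it will carry that question. With unequal windows, the difference between columns mixes observation time with any true effect of repeat treatment. The mixing runs one way: it can raise the repeat column but cannot lower it.

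The display also departs from the SAP's own practice. Section 5.1 says the analysis periods were set up so that data are collected over comparable time frames. Table 5-9 applies the same 30-day window after initial, touch-up and repeat treatment to injection site responses (ISRs) and shows later ones separately. The AE display does neither.

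At stake is an avoidable apparent safety signal for repeat treatment in a pivotal device study.

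**Working it through.** The documents state no figure for this comparison, so there is none to reproduce.

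**Window lengths**
- Initial column: first month, about 30 days (SAP 5.6.3).
- Repeat column: repeat injection to study exit (Table 5-1). Exit is at the Month 4 visit, whose target in Table 6-4 is Day 121, so about 120 days for a participant who completes.
- Ratio: 120 / 30 = 4.

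**Direction.** Suppose AE risk by time since injection is the same after both treatments. Cumulative incidence over 4 months cannot be below that over 1 month, and it is higher if any first AE starts after month 1. Appendix 12.3 of the protocol counts AEs whether or not they are related to the device, so unrelated illness builds up with time. Section 9.5 also lists delayed effects, which it describes as very occasional.

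**Size.** AE rates and timing are not in the documents, so both are assumed and varied. Let p1 be the month-1 incidence and s the share of the month-1 hazard that is acute, meaning confined to month 1. The rest is constant over 4 months.

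- H1 = −ln(1 − p1)
- H4 = s·H1 + 4·(1 − s)·H1
- p4 = 1 − exp(−H4)

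For p1 = 10%, H1 = 0.1054:
- s = 0: H4 = 4 × 0.1054 = 0.4214, so p4 = 34.4%
- s = 0.5: H4 = 2.5 × 0.1054 = 0.2634, so p4 = 23.2%
- s = 0.9: H4 = 1.3 × 0.1054 = 0.1370, so p4 = 12.8%
- s = 1: H4 = H1, so p4 = 10%

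What the repeat column would show under equal safety (ratio to the initial column in brackets):

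| Initial column (p1) | s = 0 | s = 0.5 | s = 0.9 | s = 1 |
|---|---|---|---|---|
| 5% | 18.5% (3.7) | 12.0% (2.4) | 6.5% (1.29) | 5% (1.0) |
| 10% | 34.4% (3.4) | 23.2% (2.3) | 12.8% (1.28) | 10% (1.0) |
| 20% | 59.0% (3.0) | 42.8% (2.1) | 25.2% (1.26) | 20% (1.0) |

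The shape of the hazard drives the result far more than the rate does.

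**Do the TP and RP tables repair it?** No. TP is summarised in all VOLITE-treated participants (VT) and RP only in those given repeat treatment (VRT). The lengths also differ, this time the other way. At a constant rate and p1 = 10%, TP would show 1 − 0.9^6 = 46.9% over 6 months, or 1 − 0.9^7 = 52.2% over 7 months with a touch-up, against 34.4% for RP.

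**After matching.** With the same number of days in both columns, equal safety gives equal expected incidence: 10% against 10%, ratio 1.0.

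**The case against.** The case for leaving the display alone has four parts.

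- **Other safety summaries exist.** A reader might infer that the plan has no fair comparison of repeat with initial treatment. The documents do not support that. ISRs are a named safety endpoint, and Table 5-9 summarises them in matched 30-day windows. This stands, but ISR summaries cover diary symptoms and not AEs in general.
- **The distortion may be small.** A reader might infer that repeat treatment would look three to four times worse. That is only the constant-rate end of the range. Most of the AEs listed in protocol 9.5 are injection reactions, and if nearly all onsets are early the gap is slight. This stands, and it is why the size is given as a range. A gap of exactly zero needs no first AE to start after month 1, which is unlikely when unrelated AEs count.
- **A careful reader could see the cause.** Table 5-8 plans time to onset for treatment-related TEAEs, and all TEAEs are listed. The table shells are in a separate document, so column labels are unknown. It would therefore be too strong to say that the two effects cannot be separated. However, the time-to-onset summary leaves out unrelated AEs, and a listing does not correct a table.
- **The one-month cut may be deliberate.** Touch-up falls at about Day 30, so the cut may be meant to keep touch-up events out. The SAP gives no reason, and this would not explain an open-ended repeat column. It does mean that any revision must deal with touch-up.

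**Conclusion.** The mismatch is in the current SAP text and its direction is certain: under equal safety the repeat column is never lower, and it is higher whenever a first AE starts after month 1. The size cannot be derived from the documents. At an assumed 10% month-1 incidence, the repeat column ranges from 10% (all acute) to 34.4% (constant rate). These figures assume the same hazard after each treatment, full follow-up to Month 4, and risk that does not rise with time. Early exits would shrink the gap.

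The consequence is limited. A reader might infer that trial conclusions are at risk or that harm is hidden. Neither follows: the display is descriptive, has no test, does not touch the primary or secondary analyses, and errs towards overstating AEs after repeat treatment. It should be corrected because it invites a wrong reading and the correction is cheap.

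**What to change.** In SAP 5.6.3:

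- Limit both columns to AEs with onset in the same number of days after injection, in the same VRT participants. An example is injection day to Day 30, counting injection day as Day 1, as SAP 5.6.4 does for ISRs.
- End the initial column before any touch-up, and apply that same number of days to the participant's repeat column. A fixed window alone is not enough, because the printed touch-up window is −2/+7 days around Day 30 (protocol Table 2-4, delayed treatment) and an early touch-up could fall inside it.
- Keep the TEAE table for the whole RP as a separate table, so that late events after repeat treatment remain visible.

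A paired display of the first 4 months after each course is not a good substitute. The initial course may include a touch-up and has a Month 2 visit. Repeat treatment has no touch-up listed and no Month 2 visit.

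The cost is a sentence or two in the SAP and an onset-date filter on dates already collected. The paired display gives up late-onset AEs, which the whole-RP table still reports.

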5.6.3.1. Adverse Events of Special Interest

ISRs recorded in participant ISRs recorded in participant diaries after each treatment (initial, touch-up and repeat) will be summarized for that treatment, respectively. The diary date and time will be compared with the treatment injection ISRs recorded in participant diaries after each treatment (initial, touch-up and repeat) will be summarized for that treatment, respectively. The diary date and time will be compared with the treatment injection ISRs recorded in participant diaries after each treatment (initial, touch-up and repeat) will be summarized for that treatment, respectively. The diary date and time will be compared with the treatment injection Add analysis for adverse events of special interest. The list of adverse events of special interest can be defined in [Section 6](#) or defined in this section if the list is not too lengthy.

5.6.4. Injection Site Response

ISRs recorded in participant diaries after each treatment (initial, touch-up or repeat) and the ongoing ISR e-CRF will be summarized. The diary date and time will be compared with the treatment injection date and time recorded in the database to determine the corresponding treatment (ie, initial, touch-up, or repeat) for the purpose of analysis. If there are multiple diary entries of the same treatment period for any day, then the worse severity and maximum duration

JUVÉDERM VOLITE™ XC

will be included in the summary for the corresponding symptom(s) analyzed. The descriptive statistics will be tabulated for the endpoints listed in Table 5-9 for the initial treatment, touch-up treatment, and repeat treatment periods by pre-defined symptoms.

Table 5-9 **Injection Site Response Analyses**

Endpoint	Description	Timing	Methodology
ISR severity	
Maximum reported severity for 2 summaries listed below:
 
 Up to 30 days after the treatment (initial, touch-up or repeat) based on diary data only Beyond 30 days after the (initial, touch-up or repeat) treatment across the diary and ongoing ISR eCRF 	Initial, Touch-up, Repeat	Frequency counts and percentages
ISR duration	
Duration from first instance of the symptom to the last instance of the symptom within the treatment period for 2 summaries listed below:
 
 Up to 30 days after the treatment (initial, touch-up or repeat): duration is derived as date of last ISR minus date of first ISR plus one based on the diary data between the date of corresponding treatment and 30 days after it on the participant level, regardless of the side of cheek. Beyond 30 days after the (initial, touch-up or repeat) treatment: duration is calculated as the last minus the first ISR occurrence date plus one based on all data collected from diary and ongoing ISR eCRF. 	Initial, Touch-up, Repeat	Frequency counts and percentages

Other symptoms of ISR entered in the e-diary by participants will be coded into medical terminologies by the medical safety physician. Other ISRs with “No”, “None”, or texts with a similar meaning will be coded as “n/a”. If other ISRs are coded as one of the prespecified symptoms (ie., redness, pain after injection, tenderness to touch, firmness, lumps/bumps, bruising, itching, and discoloration), then the participant will be counted only once based on the maximum severity and duration across the pre-specified symptom entries and the coded terms. Other symptoms of ISR that were coded into the terms beyond the list of pre-specified symptoms will be summarized under “Other symptoms” in the summary tables for ISR. If a participant reported more than one non-prespecified terms of “other ISR”, the participant will be counted once in the summary of “Other symptoms” for that treatment. The free texts entered by the participant, and the coded terms for “other symptoms” will be included in the data listing.

ISR day will be derived as ISR date – most recent treatment date + 1.

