Inclusion/Exclusion criteria (TI, EI, Subject). Exclude ACSS assessment and FACE-Q Satisfaction with Skin assessment if Randomization does not occur during this visit^b	X
Urine pregnancy test ^c	X

^a Includes blood pressure (systolic and diastolic) while subject is seated, pulse rate, and temperature.

^b ACSS assessment by TI and FACE-Q Satisfaction with Skin assessment by Subject are to be performed only at Randomization visit. Note: it is possible the subject will subsequently be deemed ineligible for the study once these assessments are performed at the Randomization visit.

^c For female subjects of childbearing potential; administered and confirmed negative. A female subject is not considered of childbearing potential if she has been postmenopausal for at least 1 year or does not have a uterus at the time of study entry.

Table 2-2 Treatment Group Procedures

^a Randomization must occur within 30 days of screening; screening visit and randomization visit can occur on the same day if subjects do not require washout. If screening and randomization visits occur on the same day, inclusion/exclusion criteria and urine pregnancy testing need not be repeated.

b The TI may perform a touch-up treatment, 30 days after initial treatment, if the TI determines that optimal correction was not achieved with initial treatment. If no touch-up treatment is performed, Day 30 visit becomes Month 1 visit.

c Study exit visit is at Month 6 for subjects not receiving repeat treatment. If repeat treatment is performed, Month 6 will be repeat treatment visit, and exit visit will be at Month 4 after repeat treatment.

^d For female subjects of childbearing potential; administered and confirmed negative prior to randomization/treatment. A female subject is not considered of childbearing potential if she has been postmenopausal for at least 1 year or does not have a uterus at the time of study entry.

e Randomization and initial treatment for the treatment group must occur on the same day.

On treatment days, vision assessments will be performed before treatment and approximately 30 minutes after treatment.

The treatment procedure is to be performed after all effectiveness assessments and 2D facial imaging.

h The 30-day daily safety e-diaries are to be completed following each treatment starting on the day of treatment and are considered complete if all days are completed until the Day 30/Month 1 visit.

Table 2-3 Control Group Procedures (No-Treatment Period)

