^b The TI may perform a touch-up treatment, 30 days after initial treatment, if the TI determines that optimal correction was not achieved with initial treatment. If no touch-up treatment is performed, Day 30 visit becomes Month 1 visit.

^c For female subjects of childbearing potential; administered and confirmed negative prior to treatment. A female subject is not considered of childbearing potential if she has been postmenopausal for at least 1 year or does not have a uterus at the time of study entry.

^d On treatment days, vision assessments will be performed before treatment and approximately 30 minutes after treatment.

^e The treatment procedure is to be performed after all effectiveness assessments and 2D facial imaging.

^f The 30-day daily safety e-diaries are to be completed following each treatment starting on the day of treatment and are considered complete if all days are completed until the Day 30/Month 1 visit.

3. Introduction

JUVÉDERM VOLITE™ XC (with lidocaine) is an HA-based injectable gel dermal filler for improvement in facial skin smoothness to meet an unmet need for this indication.

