5.6.6. Other Safety Endpoints

Other safety endpoints include the line change on Snellen visual acuity, confrontation visual fields, ocular motility assessments, and the overall converted score of FACE-Q Recovery Early Life Impact questionnaire (see [Section 6.5.5](#) and [Section 6.5.6](#)).

The number of line change based on Snellen visual acuity will be calculated using the formula below and rounded to the nearest integer. Baseline in the below formula is the pre-treatment value on or before the most recent treatment.

$$\text{Line change} = 10 \times [\log_{10} (d_{\text{baseline}}/20) - \log_{10} (d_{\text{follow-up}}/20)]$$

where d_{baseline} = denominator of the Snellen equivalent unit at baseline,

$d_{\text{follow-up}}$ = denominator of the Snellen equivalent unit at follow-up visit

Line change of visual acuity, confrontation visual fields, and ocular motility assessments assessed by the TI (or designee) will be summarized by descriptive statistics. The overall converted score of FACE-Q Recovery Early Life Impact questionnaire calculated based on the conversion table will be summarized by descriptive statistics.

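### SAP 5.6.4 has no rule for symptoms already present at touch-up, so the touch-up ISR table mixes new reactions with ones carried over from the initial injection

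*SAP*

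**What the plan says.** Protocol Table 2-2, footnote b, which is repeated for the control group under Table 2-4, states: "The TI may perform a touch-up treatment, 30 days after initial treatment". On the diary, the protocol states: "The 30-day daily safety e-diaries are to be completed following each treatment starting on the day of treatment". Under Protocol 9.4 the diary is kept for each cheek, and ISRs still present when it ends go on an ongoing-ISR eCRF and are followed to resolution where possible. Protocol 10.3.2 promises ISR severity and duration separately for initial, touch-up and repeat treatments.

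SAP 5.6.4 links a diary entry to a treatment by comparing its date and time with the "treatment injection date and time recorded in the database to determine the corresponding treatment (ie, initial, touch-up, or repeat"). It also states: "ISR day will be derived as ISR date – most recent treatment date + 1".

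In SAP Table 5-9, the duration row is defined as "Duration from first instance of the symptom to the last instance of the symptom within the treatment period". The summary up to 30 days is "based on the diary data between the date of corresponding treatment and 30 days after it". The beyond-30-day duration is "the last minus the first ISR occurrence date plus one based on all data collected from diary and ongoing ISR eCRF".

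**The concern.** The allocation rule looks only at when an entry was made. It has no condition on onset, worsening or pre-injection status. Touch-up comes at the point where the two diaries meet, so slow-resolving symptoms such as lumps, firmness or discoloration can run from one diary into the next. Such a symptom is then counted against the touch-up injection, and its severity can set the maximum severity shown for touch-up.

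A reader of the touch-up table would take it as the reaction profile of the second injection. As specified, it shows that profile plus whatever remained from the first, with no way to separate them. The protocol's promise of separate summaries is met in layout but only partly in content.

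**Working it through.** The plan states no ISR figure to reproduce. The check applies the written rules to a timeline and then sizes the touch-up group.

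**1. Rules side by side.**
- Allocation: diary date and time against injection date and time (SAP 5.6.4).
- Day count: restarts at the most recent treatment (SAP 5.6.4).
- Touch-up: about 30 days after initial treatment, with a new diary that day (Protocol Tables 2-2 and 2-4, footnotes).
- Carry-over, onset or worsening rule for ISRs: none found in either document.

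**2. Hypothetical timeline.** Let the initial treatment be study day 1 and the touch-up study day 31 (30 days later). One unbroken lump is present on study days 2 to 50.
- True duration: 50 − 2 + 1 = 49 days.
- Diary entries assigned to initial treatment: days 2 to 30, so 30 − 2 + 1 = 29 days.
- Diary entries assigned to touch-up: days 31 to 50, so 50 − 31 + 1 = 20 days.
- ISR day of the first touch-up entry: 31 − 31 + 1 = 1.

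The lump therefore enters the touch-up table as a 20-day reaction present from ISR day 1, although it began 29 days before that injection. If the ongoing-ISR eCRF carries it to resolution as an initial-treatment record, the beyond-30-day summary also shows it for initial treatment at 49 days. One reaction then appears under two treatments.

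**3. Safeguards elsewhere in the SAP.** For visual acuity (SAP 5.6.6), baseline is "the pre-treatment value on or before the most recent treatment", so change is measured against the state just before each injection. For adverse events (SAP 5.6.3), an event must have begun or worsened after first administration. Neither condition is applied to ISRs.

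**4. Size of the touch-up group.** Protocol 3.2 reports touch-up in 31 of 131 subjects (31/131 = 23.7%, as stated) and 46 of 261 cheeks (46/261 = 17.6%, as stated). Those subjects could also be treated in the forehead and neck, so the number with a cheek touch-up lies between 46/2 = 23 and 31. The plan expects 119 + 28 = 147 treated participants. If the same share applied:
- lower: 147 × 23/131 = 25.8, about 26;
- upper: 147 × 31/131 = 34.8, about 35.

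One carried-over participant with no new instance of the symptom adds 1/35 = 2.9 to 1/26 = 3.8 percentage points to that symptom's touch-up rate. This is the weight of one participant, not an estimate of the bias. No carry-over rate is given, and none is assumed.

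**The case against.** Assigning every post-injection entry to the most recent injection is simple and reproducible, and it does not undercount touch-up reactions. Visual acuity is a change score that needs a baseline, whereas an ISR is recorded as presence and maximum severity, so the analogy is imperfect. Table specifications are in a separate document, which may say more. No record is lost: ongoing ISRs are followed on the eCRF, and those the treating investigator judges to be adverse events are reported as such. No hypothesis test, effectiveness endpoint or sample size depends on these tables. The touch-up share used for scale comes from a product without lidocaine that was also used in the forehead and neck.

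All of this stands as a limit on severity. It does not remove the mixing, because nothing in the SAP separates a persisting symptom from a new one.

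A reader might go further and infer from Table 5-9 that durations will be wrong: either a persisting reaction is cut at touch-up and drops out of the beyond-30-day summary, or two short reactions, one after each injection, are joined into one long one. The documents do not support either inference. The first needs a rule that truncates eCRF records at touch-up. The SAP states none: its date-and-time rule concerns diary entries, and the beyond-30-day summary draws on the ongoing-ISR eCRF, which follows reactions to resolution. The second sets aside both the allocation rule and the row's own limit to the treatment period, which keep reactions after different injections apart.

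**Conclusion.** The concern holds for attribution. As written, the touch-up ISR table combines new reactions with those persisting from the initial injection. This follows directly from the stated rules and needs only that a persisting symptom is entered in the second diary.

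The number affected is unknown. Any scale beyond the weight of a single participant rests on the assumption that the feasibility touch-up share carries over. The effect is confined to descriptive ISR incidence, severity and duration for touch-up, and severity is low. Duration errors in the beyond-30-day summary are not established; for that part, only clearer wording is warranted.

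**What to change.** Keep the all-entries touch-up and repeat ISR tables as planned, and add the following to SAP 5.6.4.

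1. **Flag.** For touch-up, flag a symptom recorded on the last diary day before the injection (by cheek), or open on the ongoing-ISR eCRF at the injection. For repeat treatment, use the eCRF only, because the previous diary ended months earlier.
2. **Added table.** Show new-or-worsened ISRs beside the all-entries table: symptoms not flagged, or with severity above the pre-injection level.
3. **Wording in Table 5-9.** State that an ISR continuing without a gap through a later injection keeps its original treatment and start date, with its eCRF stop date, and that reactions after different injections are not joined.

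The cost is a short SAP edit and modest programming, using data already collected. The documents do not say whether the ongoing-ISR eCRF records the side, so that flag may have to be at participant level. The main downside is that a new reaction of the same severity, on a cheek with a persisting symptom, is classed as carried over in the added table. The all-entries table still shows it.
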